1.3 Study Rationale

Until recently, microsatellite stable (MSS) recurrent endometrial cancer was a disease of high unmet medical need. In 2018, the US Food and Drug Administration (FDA) granted a breakthrough designation and, in 2019, an accelerated approval to the combination of the immune checkpoint inhibitor, pembrolizumab, and the oral anti-angiogenic agent, lenvatinib.

With an objective response rate (ORR) at 24 weeks of 36.2% (95% CI, 26.5% to 46.7%) in patients with MSS tumors (n = 94), and a median duration of response (DOR) of 21.2 months (95% CI, 7.6 months to not estimable), compared to historical ORR of 12-15% and DOR of 3-6 months, these results were exciting and led to widespread adoption of the combination in clinical practice. This enthusiasm was despite the incidence of grade 3 or 4 treatment-related adverse events (AEs) in 83/124 (66.9%) patients--most commonly hypertension and diarrhea—a 33% discontinuation rate for toxicity, and absence of quality of life data. A confirmatory phase 3 trial of lenvatinib/pembrolizumab versus standard chemotherapy in the second-line setting recently reported a progression-free survival (PFS) and overall survival (OS) advantage for the lenvatinib/pembrolizumab combination but again with significant AEs and treatment discontinuation (33% vs 8% for chemotherapy). On July 21, 2021, the FDA approved pembrolizumab in combination with lenvatinib for patients with advanced endometrial carcinoma that is not microsatellite instability-high (MSI-H) or mismatch repair deficient (dMMR), who have disease progression following prior systemic therapy in any setting and are not candidates for curative surgery or radiation.

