2.2 Secondary Objectives

- 2.2.1 Determine median PFS in the study population
- 2.2.2 Determine the incidence of treatment-related AEs in the study population
- 2.2.3 Determine the number of patients who discontinue treatment due to treatment-related AEs

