3.3 Secondary Endpoints

- 3.3.1 Proportion of patients who are alive and have not had disease progression or relapse following last dose of study treatment
- 3.3.2 Using criteria in the National Cancer Institute Common Terminology Criteria for Adverse Events Version 5.0 (CTCAE v5.0), all AEs captured as described in Section [8.4](#).
- 3.3.3 Number of patients who discontinue treatment due to treatment-related AEs.

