13 STATISTICAL CONSIDERATIONS

13.1 Study Design and Analysis

Primary Analysis: The binary outcome ORR: will be estimated with a sample proportion and 95% Wilson confidence intervals. The ORR will be estimated in unadjusted and adjusted manners, where in the latter case we use logistic regression to model the outcome against fixed effects for patient characteristics and disease biomarkers, using a Bernoulli distribution and logit link function, including a set of measurements that minimize the Bayesian Information Criterion.

Secondary Analyses: OS is calculated as the time between treatment start date until date of death from any cause or until censoring. PFS is calculated as the time between treatment start date until occurrence of disease progression or until censoring. The Kaplan-Meier product limit approach will be used to estimate step functions for OS and PFS. Proportional hazard modeling will be used to estimate mean survival time in both unadjusted and adjusted manners, where in the latter case we account for patient characteristics and disease biomarkers.

Safety Analyses: Times to toxicity, dose reduction, or drug discontinuation will be used as safety outcomes. Each measure is calculated as the time between treatment start date until event occurrence or until censoring. These measures will be summarized using proportional hazards regression, and visually present the event curves with cumulative incidence curves.

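### The safety analysis in 13.1 is not specified so as to produce the treatment-related AE incidence (2.2.2) or the number discontinuing for treatment-related AEs (2.2.3, 3.3.3)

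*Combined protocol and SAP*

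**What the plan says.** The safety material sits in three places.

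- **Objectives (2.2).** 2.2.2 is to "Determine the incidence of treatment-related AEs in the study population". 2.2.3 is to "Determine the number of patients who discontinue treatment due to treatment-related AEs".
- **Endpoints (3.3).** 3.3.2 takes "all AEs captured as described in Section" 8.4, graded by CTCAE v5.0, with no attribution filter and no summary measure. 3.3.3 is the "Number of patients who discontinue treatment due to treatment-related AEs", which matches 2.2.3.
- **Analysis (13.1, Safety Analyses).** "Times to toxicity, dose reduction, or drug discontinuation will be used as safety outcomes". On timing: "Each measure is calculated as the time between treatment start date until event occurrence or until censoring". On method: "These measures will be summarized using proportional hazards regression", with cumulative incidence curves as the display.

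Three other sections bear on this. Section 8.1.6 sets out five attribution levels but does not say which count as treatment-related. Section 8.3 evaluates AEs from signature of consent, whereas the clock in 13.1 starts at treatment. Section 1.3 gives the figures that a reader will compare with: an "incidence of grade 3 or 4 treatment-related adverse events (AEs) in 83/124 (66.9%) patients", and a 33% discontinuation rate for toxicity.

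**The concern.** The objectives are counts and proportions of patients with events attributed to treatment. The analysis is a set of times to event, with attribution absent from all three. Someone following 13.1 literally would report a hazard model for an undefined event, and a discontinuation curve that mixes toxicity with progression. Neither is what 2.2.2, 2.2.3 or 3.3.3 asks for.

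Section 3.1 gives safety equal billing with efficacy, in a population described as under-represented in two registration trials. The comparison figures in 1.3 are both proportions of patients. Without a matching proportion, the trial's safety result cannot be read against them. If attribution and grade cut-offs are left open, they will be chosen after the data of an open-label study have been seen.

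**Working it through.** **1. Objectives, endpoints and analysis side by side**

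| Question | Objective | Endpoint | Analysis in 13.1 |
|---|---|---|---|
| AEs | Incidence, treatment-related (2.2.2) | All AEs, no summary measure (3.3.2) | Time to toxicity; attribution, grade and first-or-any event not stated |
| Discontinuation | Number, for treatment-related AEs (2.2.3) | The same number (3.3.3) | Time to drug discontinuation; cause not stated |

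The last column does not lead back to the first. On discontinuation, 3.1 has patients treated until progression or unacceptable toxicity. A time to discontinuation with no cause attached therefore counts progression as an event.

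**2. What the stated methods estimate**

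Proportional hazards regression estimates hazard ratios between covariate levels. This trial has no treatment contrast, and the safety paragraph names no covariates. A fit without covariates still gives a baseline cumulative hazard H(t), and 1 − exp(−H(t)) can be read as a probability. If competing events are censored, that quantity is not the proportion of patients who have the event.

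To show the size, assume constant hazards a (event) and c (competing: death, or stopping for progression). These values are assumptions, not taken from the documents. Take t = 7 months, the median treatment duration quoted in 9.2.11.

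- Competing events censored: 1 − exp(−a·t)
- True cumulative incidence: [a/(a + c)]·[1 − exp(−(a + c)·t)]

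| a per month | c per month | Censored | True | Excess (points) |
|---|---|---|---|---|
| 0.05 | 0.10 | 29.5% | 21.7% | 7.9 |
| 0.10 | 0.10 | 50.3% | 37.7% | 12.7 |
| 0.20 | 0.10 | 75.3% | 58.5% | 16.8 |

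For the middle row: 1 − exp(−0.7) = 0.503, and 0.5 × (1 − exp(−1.4)) = 0.377. A cumulative incidence curve that treats these events as competing gives the true column. Section 13.1 does not say what is censored and what competes.

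**3. Precision of the proportions the objectives call for**

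The only design figure in section 13 is the ±0.1 margin for ORR at n = 100 and p = 0.5. It reproduces: 1.96 × √(0.25/100) = 0.098, and the Wilson half-width is 0.096. No figure is stated for safety.

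The Wilson interval, which 13.1 already uses for ORR, has

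- centre (p + z²/2n)/(1 + z²/n)
- half-width z·√[p(1 − p)/n + z²/4n²]/(1 + z²/n)

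with z = 1.96 and n = 100.

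- The benchmark 83/124 = 66.9% reproduces. The nearest count, 67/100, gives centre 0.6892/1.0384 = 0.664 and half-width 0.0907, so 57.3% to 75.4%.
- For 33/100, the interval is 24.6% to 42.7%.
- For 90/100, it is 82.6% to 94.5%.

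The half-width does not exceed the 9.6 points found at p = 0.5, so the planned 100 patients support these estimates as well as they support ORR.

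**The case against.** The strongest reply is that nothing needed is excluded. All AEs is a superset of treatment-related AEs, grade and attribution are both defined, 3.3.3 restates 2.2.3 correctly, and most teams tabulate AEs by custom. The safety paragraph also covers three outcomes and includes cumulative incidence curves, which are incidence estimates. Much of this stands. It rules out saying that the endpoint contradicts the objective, or that the plan can yield no incidence at all. It does not supply a definition of the event, a rule for attribution or a commitment to the proportion.

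Several stronger readings are tempting but are not supported:

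- **That the hazard model would be empty.** The safety paragraph is silent on covariates, while the secondary-analysis paragraph plans adjusted and unadjusted models. Even a fit without covariates gives a baseline hazard. The fault is the target, not an absence of output.
- **That toxicity means AEs of any cause.** The protocol uses the word both for AEs in general (7.2, 8.4) and for harm from treatment (1.3, 4.1.13). It is ambiguous, which is the reason to define it.
- **That any-cause, any-grade incidence would approach 100%.** Table 7 has four terms at 64% to 65%, but the overlap is not given. The proportion with at least one of them could lie anywhere from 65% to 100%.
- **That this regimen's toxicity has never been measured in Black patients.** Section 3.1 says only that the population was under-represented.

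One practical objection also stands in part. Section 8.4 generally allows only the highest grade within a study segment to be recorded, and does not define the segment. That suits a worst-grade proportion but may not preserve the onset dates that a time-to-event curve needs.

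**Conclusion.** The point holds as a specification gap. Both safety objectives lack a planned analysis that estimates them, and the stated method targets different quantities. The primary endpoint is not affected.

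The size of the problem is the lack of two pre-specified estimates, each of which 100 patients would give to within about 9 to 10 points. If an incidence were instead read from curves with competing events censored, the overstatement would be about 8 to 17 points under the assumed hazards. Those hazards are illustrative only.

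The conclusion assumes about 100 treated patients and that attribution is recorded for each AE; 8.1.6 defines the scale without saying how it is captured. Comparison with 66.9% can only be descriptive: that figure covers 124 patients, while 1.3 gives 94 with microsatellite-stable tumors, the group this trial enrols. It is also a grade 3 or 4 figure, so a combined grade 3 to 5 rate would not match it.

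**What to change.** In 13.1, make the main safety summary the number and proportion of treated patients with at least one treatment-related AE from first dose, by term and worst grade, with 95% Wilson intervals.

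- State that possible, probable and definite attribution count as treatment-related, and align 3.3.2 with 2.2.2.
- Show grade 3-4 separately, so that it can be set beside 83/124 (66.9%), and report grade 5 as well.
- Report the number and proportion for 3.3.3 in the same way, beside the 33% figure. State whether stopping one of the two drugs counts as discontinuation in this analysis.
- Keep all-cause AEs as a supporting table.
- Keep the cumulative incidence curves, with the event defined and with death and stopping for progression named as competing events, not censored.
- Use hazard regression only for associations with named covariates.

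The cost is wording and slightly more analysis work, with N unchanged. Grade and attribution are already defined (8.1.4, 8.1.6), and 6.4 already requires the reason for stopping treatment to be recorded. Before the curves are relied on, confirm that the eCRF holds attribution and onset date for each event.

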13.2 Sample Size/Accrual Rates

As the goal of this proposal is to estimate ORR, we will not formally power for hypothesis testing. With 100 subjects (and conservatively assuming a 0.5 ORR for maximum variability), we would be able to estimate the ORR with a margin of error of ± 0.1 .

This study is expected to be open to accrual at a total of 10 sites across the US within 24 months of its initial approval at the coordinating site, VCU Massey Cancer Center. Each site is anticipated to accrue an average of 1 patient every 2 to 3 months. The total period of study recruitment is therefore anticipated to occur over a period of 25 to 42 months, with recruitment complete by July 1, 2025.

14 DATA AND SAFETY MONITORING PLAN (DSMP)

While patients are on treatment, the principal investigator, study team members (e.g., site investigators, research nurses, clinical research associates) and Coordinating Center staff will meet at least monthly to review study status. The biostatistician will review data with the principal investigator and Coordinating Center staff at least quarterly. This review will include, but not be limited to, reportable events and an update of the ongoing study summary that describes study progress in terms of the study schema. All meetings, including attendance, are documented.

14.1 Monitoring and Auditing

14.1.1 MCC Compliance Office

Compliance specialists in the MCC Compliance Office will provide monitoring and auditing for this study.

14.1.2 Data Safety and Monitoring Committee

The study will be reviewed by the MCC DSMC initially according to the risk level specified by the MCC Protocol Review and Monitoring Committee (PRMC) and then according to a schedule based on study status and quality indicators. The DSMC will review reports provided by the principal investigator/study team and the MCC Compliance Office focusing on data integrity and patient safety.

15 REGULATORY COMPLIANCE AND ETHICS

15.1 Ethical Standard

This study will be conducted in conformance with the principles set forth in *The Belmont Report: Ethical Principles and Guidelines for the Protection of Human Subjects of Research* (US National Commission for the Protection of Human Subjects of Biomedical and Behavioral Research, April 18, 1979).

15.2 Regulatory Compliance

This study will be conducted in compliance with the clinical trial protocol and with federal regulations, as applicable, including: 21 CFR 50 (Protection of Human Patients/Informed Consent); 21 CFR 56 (Institutional Review Boards); 21 CFR 312 (IND Application); and 45 CFR 46 Subparts A (Common Rule), B (Pregnant Women, Human Fetuses and Neonates), C (Prisoners), and D (Children).

15.3 Institutional Review Board

The VCU IRB, which is registered with the Office for Human Research Protections (OHRP), must review and approve the protocol, the associated informed consent document, and recruitment material (if any). Any amendments to the protocol or consent form must also be approved.

15.4 Informed Consent Process

Informed consent is a process that is initiated prior to the individual's agreeing to participate in the study and continues throughout the individual's study participation. Discussion of risks and possible benefits of this therapy will be provided to patients and their families. Consent forms describing the study interventions, study procedures, and risks are given to the patient and written documentation of informed consent is required prior to starting intervention/administering study product.

Consent forms will be IRB-approved and the patient will be asked to read and review the document. Upon reviewing the document, the investigator will explain the research study to

the patient and answer any questions that may arise. The patient will sign the informed consent document prior to any procedures being done specifically for the study. Patients should have the opportunity to discuss the study with their surrogates or think about it prior to agreeing to participate. Patients may withdraw consent at any time throughout the course of the trial. A copy of the informed consent document will be given to patients for their records; the original consent form will be maintained in the research records.

15.5 Patient Confidentiality

Patient confidentiality is strictly held in trust by the principal investigator, participating investigators, staff, and the sponsor and its agents. This confidentiality includes the clinical information relating to participating patients, as well as any genetic or biological testing.

The study protocol, documentation, data, and all other information generated will be held in strict confidence. No information concerning the study or the data will be released to any unauthorized third party without prior written approval of the principal investigator.

The participating site will allow access to all source data and documents for the purposes of monitoring, audits, IRB review, and regulatory inspections. Source documents provided to the Coordinating Center for the purpose of auditing or monitoring will be de-identified and labeled with the study number, patient ID number, and patient initials.

The study monitor or other authorized representatives of the principal investigator may inspect all documents and records required to be maintained by the investigator, including but not limited to, medical records (office, clinic, or hospital) and pharmacy records for the patients in this study. The clinical study site will permit access to such records.

16 DATA COLLECTION AND MANAGEMENT

16.1 Data Management Responsibilities

The principal investigator is responsible for: (i) the overall conduct of the investigation, (ii) ongoing review of trial data including all safety reports, and (iii) reporting SAEs and UPs as required in Section [8](#).

16.2 Case Report Forms and Data Collection

MCC will provide standard electronic CRFs (eCRFs) and create study-specific eCRFs to be able to capture all information required by the protocol. The eCRFs will be approved by the Coordinating Center to ensure the most effective data acquisition.

The investigator(s) and study coordinator(s) must maintain source documents for each patient in the study. All information on eCRFs will be traceable to these source documents, which are generally maintained in the patient's file.

All eCRFs should be completed and available for collection within a timely manner, preferably no more than 5 days after the patient's visit.

16.3 OnCore Data Entry

Data will be entered into MCC's OnCore database on an ongoing basis by all participating centers via remote access. Sites are responsible for updating data to allow for data compilation and review. Electronic data submissions will be reviewed periodically for data timeliness and accuracy. Sites will be queried periodically and significant problems with delinquency or accuracy may result in suspension of enrollment at a site.

16.4 Study Record Retention

As applicable, study records will be maintained a minimum of 5 years beyond the publication of any abstract or manuscript reporting the results of the protocol or submission of a final report to clinicaltrials.gov.

APPENDIX 1. PERFORMANCE STATUS CRITERIA

ECOG Performance Status Scale		Karnofsky Performance Scale	
Grade	Description	Percent	Description
0	Normal activity. Fully active, able to carry on all pre-disease performance without restriction.	100	Normal, no complaints, no evidence of disease.
		90	Able to carry on normal activity; minor signs or symptoms of disease.
1	Symptoms, but ambulatory. Restricted in physically strenuous activity, but ambulatory and able to carry out work of a light or sedentary nature (eg, light housework, office work).	80	Normal activity with effort; some signs or symptoms of disease.
		70	Cares for self; unable to carry on normal activity or to do active work.
2	In bed < 50% of the time. Ambulatory and capable of all self-care, but unable to carry out any work activities. Up and about > 50% of waking hours.	60	Requires occasional assistance, but is able to care for most of his/her needs.
		50	Requires considerable assistance and frequent medical care.
3	In bed > 50% of the time. Capable of only limited self-care, confined to bed or chair > 50% of waking hours.	40	Disabled; requires special care and assistance.
		30	Severely disabled; hospitalization indicated. Death not imminent.
4	100% bedridden. Completely disabled. Cannot carry on any self-care. Totally confined to bed or chair.	20	Very sick, hospitalization indicated. Death not imminent.
		10	Moribund, fatal processes progressing rapidly.
5	Dead.	0	Dead.

APPENDIX 2. DOSE MODIFICATION AND TOXICITY MANAGEMENT FOR IMMUNE-RELATED ADVERSE EVENTS (irAEs) ASSOCIATED WITH PEMBROLIZUMAB

Immune-related Adverse Event	Toxicity Grade or Conditions (CTCAE v4.0)	Action Taken with Pembrolizumab	irAE Management with Corticosteroids and Other Therapies	Monitor and Follow-up
General instructions:				
Corticosteroid taper should be initiated upon AE improving to Grade 0 or 1 and continue to taper over at least 4 weeks. For situations where pembrolizumab has been withheld, pembrolizumab can be resumed after AE has improved to grade 0 or 1 and corticosteroid has been tapered. Pembrolizumab should be permanently discontinued if AE does not resolve within 12 weeks of last dose or corticosteroids cannot be reduced to ≤ 10 mg prednisone or equivalent per day within 12 weeks.				
Pneumonitis	Grade 2	Withhold	Administer corticosteroids (initial dose of 1-2 mg/kg prednisone or equivalent) followed by taper. Add prophylactic antibiotics for opportunistic infections.	Monitor for signs and symptoms of pneumonitis. Evaluate patients with suspected pneumonitis with radiographic imaging and initiate corticosteroid treatment.
	Grade 3 or 4, or recurrent grade 2	Permanently discontinue		
Diarrhea / Colitis	Grade 2 or 3	Withhold	Administer corticosteroids (initial dose of 1-2 mg/kg prednisone or equivalent) followed by taper. Patients with diarrhea/colitis should be advised to drink liberal quantities of clear fluids. If sufficient oral fluid intake is not feasible, fluid and electrolytes should be substituted via IV infusion.	Monitor subjects for signs and symptoms of enterocolitis (i.e., diarrhea, abdominal pain, blood or mucus in stool with or without fever) and of bowel perforation (i.e., peritoneal signs and ileus). Patients with grade ≥ 2 diarrhea suspecting colitis should consider GI consultation and performing endoscopy to rule out colitis.
	Grade 4	Permanently discontinue		
AST / ALT elevation or increased bilirubin	Grade 2	Withhold	Administer corticosteroids (initial dose of 0.5 - 1 mg/kg prednisone or equivalent) followed by taper.	Monitor with liver function tests (consider weekly or more frequently until liver enzyme value returned to baseline or is stable).
	Grade 3 or 4	Permanently discontinue		
Type 1 diabetes mellitus (T1DM) or Hyperglycemia	Newly onset T1DM or grade 3 or 4 hyperglycemia associated with evidence of β -cell	Withhold	Initiate insulin replacement therapy for patients with T1DM. Administer anti-hyperglycemic in patients with hyperglycemia.	Monitor patients for hyperglycemia or other signs and symptoms of diabetes.

Immune-related Adverse Event	Toxicity Grade or Conditions (CTCAE v4.0)	Action Taken with Pembrolizumab	irAE Management with Corticosteroids and Other Therapies	Monitor and Follow-up
	failure			
Hypophysitis	Grade 2	Withhold	Administer corticosteroids and initiate hormonal replacements as clinically indicated	Monitor for signs and symptoms of hypophysitis (including hypopituitarism and adrenal insufficiency).
	Grade 3 or 4	Withhold or permanently discontinue		
Hyperthyroidism	Grade 2	Continue	Treat with nonselective beta-blockers (e.g., propranolol) or thionamides as appropriate	Monitor for signs and symptoms of thyroid disorders.
	Grade 3 or 4	Withhold or permanently discontinue		
Hypothyroidism	Grade 2-4	Continue	Initiate thyroid replacement hormones (e.g., levothyroxine or liothyroinine) per standard of care	Monitor for signs and symptoms of thyroid disorders.
Nephritis and Renal dysfunction	Grade 2	Withhold	Administer corticosteroids (prednisone 1-2 mg/kg or equivalent) followed by taper	Monitor changes of renal function.
	Grade 3 or 4	Permanently discontinue		
Myocarditis	Grade 1 or 2	Withhold	Based on severity of AE administer corticosteroids	Ensure adequate evaluation to confirm etiology and/or exclude other causes.
	Grade 3 or 4	Permanently discontinue		
All other immune-related AEs	Intolerable/persistent grade 2	Withhold	Based on type and severity of AE administer corticosteroids	Ensure adequate evaluation to confirm etiology and/or exclude other causes.
	Grade 3	Withhold or discontinue based on the type of event. Events that require discontinuation include but are not limited to: Gullain-Barre Syndrome, encephalitis		

Immune-related Adverse Event	Toxicity Grade or Conditions (CTCAE v4.0)	Action Taken with Pembrolizumab	irAE Management with Corticosteroids and Other Therapies	Monitor and Follow-up
	Grade 4 or recurrent grade 3	Permanently discontinue		

Withholding or permanently discontinuing pembrolizumab is at the discretion of the investigator or treating physician.

For patients with grade 3 or 4 immune-related endocrinopathy where withholding of pembrolizumab is required, pembrolizumab may be resumed when the AE improves to grade ≤ 2 and is controlled with hormonal replacement therapy or metabolic control is achieved (in the case of T1DM).

AE = adverse event, CTCAE = Common Terminology Criteria for Adverse Events, ALT = alanine aminotransferase, AST = aspartate aminotransferase, GI = gastrointestinal, irAE = immune-related adverse event, IV = intravenous, T1DM = Type 1 diabetes mellitus.

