6.3.1 Supportive Care

- Patients should receive appropriate supportive care measures as deemed necessary by the treating physician
- Supportive care measures for the management of AEs with potential immunologic etiology, ie, irAEs, are outlined in [Appendix 2](#).

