7.4 Pembrolizumab Treatment Modification

Dose modifications for pembrolizumab are based on current prescribing information.

No dose reduction for pembrolizumab is recommended. In general, withhold pembrolizumab for severe (grade 3) immune-mediated adverse reactions. Permanently discontinue pembrolizumab for life-threatening (grade 4) immune-mediated adverse reactions, recurrent severe (grade 3) immune-mediated reactions that require systemic immunosuppressive treatment, or an inability to reduce corticosteroid dose to 10 mg or less of prednisone or equivalent per day within 12 weeks of initiating steroids.

Dosage modifications for pembrolizumab for adverse reactions that require management different from these general guidelines are summarized in [Table 4](#).

Table 4: Recommended Dosage Modifications for Pembrolizumab

Adverse Reaction	Severity*	Dosage Modification
Immune-Mediated Adverse Reactions		
Pneumonitis	Grade 2	Withhold†
	Grade 3 or 4	Permanently discontinue
Colitis	Grade 2 or 3	Withhold†
	Grade 4	Permanently discontinue
Hepatitis with no tumor involvement of the liver	AST or ALT increases to more than 3 and up to 8 times ULN or Total bilirubin increases to more than 1.5 and up to 3 times ULN	Withhold†
	AST or ALT increases to more than 8 times ULN or Total bilirubin increases to more than 3 times ULN	Permanently discontinue
Hepatitis with tumor involvement of the liver‡	Baseline AST or ALT is more than 1 and up to 3 times ULN and increases to more than 5 and up to 10 times ULN or Baseline AST or ALT is more than 3 and up to 5 times ULN and increases to more than 8 and up to 10 times ULN	Withhold†
	ALT or AST increases to more than 10 times ULN or Total bilirubin increases to more than 3 times ULN	Permanently discontinue
Endocrinopathies	Grade 3 or 4	Withhold until clinically stable or permanently discontinue depending on severity
Nephritis with Renal Dysfunction	Grade 2 or 3 increased blood creatinine	Withhold†
	Grade 4 increased blood creatinine	Permanently discontinue
Exfoliative Dermatologic Conditions	Suspected SJS, TEN, or DRESS	Withhold†
	Confirmed SJS, TEN, or DRESS	Permanently discontinue
Myocarditis	Grade 2, 3, or 4	Permanently discontinue
Neurological Toxicities	Grade 2	Withhold†
	Grade 3 or 4	Permanently discontinue
Hematologic toxicity in patients with cHL or PMBCL	Grade 4	Withhold until resolution to Grades 0 or 1
Other Adverse Reactions		
Infusion-related reactions	Grade 1 or 2	Interrupt or slow the rate of infusion

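### Table 4 and Appendix 2 give conflicting default pembrolizumab actions for grade 2 myocarditis and grade 3 nephritis, and no text states which one governs

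*Combined protocol and SAP*

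**What the plan says.** Section 7.4 opens by resting pembrolizumab dose changes on the current prescribing information. It then gives general rules: hold for a grade 3 immune-mediated reaction; stop for good at grade 4, for a recurrent grade 3 reaction that needs systemic immunosuppression, or when steroids cannot be tapered in time. The exceptions go to Table 4: "Dosage modifications for pembrolizumab for adverse reactions that require management different from these general guidelines are summarized in" that table. Its myocarditis row reads "Myocarditis Grade 2, 3, or 4 Permanently discontinue". Its nephritis row puts "Grade 2 or 3 increased blood creatinine" under withhold, with a footnote that allows resumption at grade 0 to 1 after steroid taper, and reserves permanent discontinuation for grade 4.

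Appendix 2 is titled "DOSE MODIFICATION AND TOXICITY MANAGEMENT FOR IMMUNE-RELATED ADVERSE EVENTS (irAEs) ASSOCIATED WITH PEMBROLIZUMAB" and has a column for the action taken with pembrolizumab. Its myocarditis row begins "Myocarditis Grade 1 or 2 Withhold" and stops the drug for good only at grade 3 or 4. Its row for "Nephritis and Renal dysfunction" holds at grade 2 and stops for good at grade 3 or 4. Under its general instructions, once the drug has been withheld, "pembrolizumab can be resumed after AE has improved to grade 0 or 1 and corticosteroid has been tapered".

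The body text points to Appendix 2 from Section 6.3.1: "Supportive care measures for the management of AEs with potential immunologic etiology, ie, irAEs, are outlined in" that appendix. Section 7.4 does not mention it.

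**The concern.** A site that records one of these two events can open two parts of the same protocol and find different defaults. After grade 2 myocarditis, a site working from Appendix 2 may restart a drug that Table 4 ends. After grade 3 nephritis, a site working from Appendix 2 ends a drug that Table 4 would let the patient resume.

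The stake is patient safety and uniform handling across up to 10 sites. Restarting after myocarditis is the more serious half: Section 9.2.10 lists myocarditis among the clinically significant immune-mediated reactions and notes severe or fatal cases for some reactions on that list.

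**Working it through.** No arithmetic applies, and the plan states no figure to reproduce. The check is a comparison of rows, followed by a search for a rule that ranks the two sources.

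**Step 1. The rows side by side**

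| Event and nominal grade | Table 4 (Section 7.4) | Appendix 2 | Stricter source |
|---|---|---|---|
| Myocarditis, grade 2 | Stop for good | Hold; resumption allowed at grade 0 or 1 after taper | Table 4 |
| Nephritis or raised creatinine, grade 3 | Hold; resumption allowed at grade 0 to 1 after taper | Stop for good | Appendix 2 |

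The two differences run in opposite directions, so following the stricter source would mean using a different table for each event. For nephritis, Appendix 2 also departs from the general grade 3 rule in the body of Section 7.4.

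**Step 2. Is there a rule of precedence?**

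- Section 7.4 names the prescribing information and Table 4. It is silent on Appendix 2.
- Section 6.3.1 sends the reader to Appendix 2 for supportive care. It is silent on dose action.
- Section 6.4 refers to Section 8 for adverse events that require stopping treatment. Section 8 covers definitions, capture and reporting, and gives no dose action.
- Section 9.2.10 says only that the choice between holding and stopping depends on severity.
- The note under Appendix 2 leaves holding or stopping to the physician. It does not rank the tables.

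None of these states which table governs.

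**Step 3. Are the grades comparable?**

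Appendix 2 is headed CTCAE v4.0, while Sections 7.2 and 8.1.4 specify v5.0. The severity heading of Table 4 carries an asterisk with no matching note in the readable text. Table 4 grades the renal event by blood creatinine; Appendix 2 names nephritis and renal dysfunction. The comparison is therefore at the same nominal grade, not on a proven common scale. That is enough here, because sites grade once, under v5.0, and would take that grade to either table. No text offers the version difference as the reason for the different actions.

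**Step 4. How many patients?**

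This cannot be computed. Table 8 gives 7% for grade 3-4 raised creatinine, but from any cause and not split by grade. Section 9.2.10 puts myocarditis below 1%, but for all grades and including reports from other antibodies of the class. The lower bound is 0, and the documents support no upper figure.

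**Step 5. Two smaller mismatches**

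- The 12-week limit for an unresolved event runs from the start of steroids in the Table 4 footnote and from the last dose in Appendix 2.
- Appendix 2 continues pembrolizumab through grade 2-4 hypothyroidism. The endocrinopathies row of Table 4 holds or stops at grade 3 or 4 and names no exception.

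**The case against.** The best defence is that the protocol already divides the work. Section 7.4 is the section on pembrolizumab modification, it names its basis, and it cites Table 4 alone; Section 6.3.1 uses Appendix 2 for supportive care. On that reading Table 4 governs dosing. It is the better inference, and it stands as an inference. It does not close the point, because Appendix 2 announces dose modification in its title and keeps a contrary action column in force.

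A second defence is that nothing here is mandatory. Table 4 is headed as recommended, Appendix 2 only permits resumption and defers to the physician, and Section 6.4 lets the investigator stop treatment in the patient's interest. This stands as well. A reader might infer that the tables issue opposite orders and that a site cannot satisfy both. The documents do not support that: permanent discontinuation after grade 2 myocarditis, for example, is compatible with both. What remains is a conflict of defaults, and discretion needs one default to start from.

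The smaller mismatches are rightly discounted. The last dose in Appendix 2 most naturally means the last pembrolizumab dose, and its hypothyroidism row can be read as a specific exception to the general endocrinopathies row.

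**Conclusion.** The inconsistency is real and should be corrected. Its size is two event-and-grade combinations with conflicting defaults. The number of patients affected may be zero and cannot be bounded above from these documents.

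A reader might go on to infer that the conflict distorts the count of patients who discontinue for treatment-related adverse events (endpoint 3.3.3), or the response rate. The documents show neither. They give no grade-specific rate for either event and no indication of how often sites would act on one table rather than the other. The sample size and the ±0.1 margin of error for ORR do not depend on it. Nor can the conflict be expressed as a share of all dosing rules, since a common grading scale is not established.

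The conclusion assumes that the table rows were extracted correctly, which their legibility supports, and that no removed or redacted page contains a rule of precedence.

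**What to change.** Add one sentence to Section 7.4: Table 4 governs the dose action for pembrolizumab, and Appendix 2 covers treatment and monitoring of immune-related events.

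Then align the Appendix 2 myocarditis and nephritis rows to Table 4, both subject to medical review against the current prescribing information. The nephritis change relaxes a permanent stop into a hold, so it is a medical decision and more than an edit.

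In the same amendment:

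- change the Appendix 2 grading header from CTCAE v4.0 to v5.0, to match Section 7.2;
- give the 12-week limit one starting point;
- after medical review, either write the hypothyroidism exception into Table 4 or align the Appendix 2 row.

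The cost is one wording amendment with medical review. Sample size, visits and analysis do not change.
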